#### **(4) Work Proposed**

We will conduct a multi-method project with observational and interventional components and use a mixed methods analytic approach. This project is guided by REP’s pre-conditions and pre-implementation phases (see Figure 2 above). While phase 3 was initially intended to be multisite, due to feasibility and low enrollment problems at the VA Connecticut site (as evidenced by low participant recruitment and enrollment in Phase 2) we received a VA HSR&D Project modification to HSR&D to have Boston be the sole site for the RCT phase 3. The timeline for all activities is provided in bullet points below.

#### **(a-b) Timeline/Key Questions/Study Sites**

##### Timeline for Proposed Research.

- Phase 3 - Conduct RCT of RISE with WVs (n = up to 68) (Approximately September 2018- September 2020; Dissemination and implementation activities in FY2021).

##### *Study Setting*

While Phase 3 was initially intended to be multisite, due to feasibility problem identified in phases 1 and 2, the RCT was conducted at VA Boston. In consultation with the DSMB, we have decided to discontinue involvement of VA Connecticut and continue the RCT solely at VA Boston to meet the primary objective of the study.

#### **Phase 3**

##### **Specific Aims for Phase 3 Research:**

**3.** Examine the effects of RISE on WVs’ (n=60-68) individual psychosocial outcomes (e.g., empowerment, self-efficacy, health symptoms, service use, and quality of life) in an RCT that compares RISE to an information/referral condition.

Sub-aim **3a.** Evaluate the feasibility and acceptability of RISE in the context of the RCT.

#### **(c) Method and Data Analysis**

##### Aim 3

**Randomized clinical trial (RCT):** The goal of Aim 3 is to test the RISE intervention in comparison to an information/referral condition for women VA patients who have experienced past-year IPV. We selected a Hybrid Type 1 RCT design to evaluate the initial effectiveness RISE while gathering information on barriers and facilitators of implementation. We selected an information/referral comparison condition because a) this intervention is consistent with the current standard of care at the two study sites (and in the community); b) many other VA facilities are supposed to provide information and referrals for women who disclose IPV (according to VHA recommendations); and 3) an information/referral condition conforms to the US Preventive Services guidelines and to the suggestions of the Department of Health and Human Services. Participants will receive the information/referral condition for up to 60 minutes in order to standardize the comparison condition while also ensuring that women receive at least the minimum standard of care. At VA Boston, up to 68 female patients will be recruited and randomly assigned. Assuming 15% loss to follow-up based on current study estimates, we will aim to enroll 68 women to ensure sample size of n=60 for participants with post-treatment and/or follow-up assessments (i.e., at least 2 data points). To address our sub-aim, providers will be invited to participate in brief (30-minute), semi-structured qualitative interviews toward the end of the RCT to provide perspective on RISE implementation.

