## **Specific Aims**

### **Phase 3:**

Aim 3. Examine the effects of RISE on WVs' individual psychosocial outcomes with an effective-implementation Hybrid 1 RCT  that compares RISE to an information/referral condition with up to 68 female patients at VA Boston. We will collect pre-treatment, post-treatment, and 1-month follow-up patient data to examine the effects of RISE on key psychosocial outcomes.

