participation will be offered information on relevant resources within VA and the community (e.g., Passageway Program at Brigham and Women's Hospital, National DV Hotline, etc.). Patients who meet inclusion criteria will be scheduled based on participant and provider availability as soon as possible, ideally within two weeks. At this visit they will fully review and sign informed consent documents and HIPAA Authorization (see Informed Consent document and HIPAA forms attached). Because women will be asked to complete questionnaires that include demographics information about themselves and IPV exposure, participants will complete the HIPAA authorization form. Patients will complete the pre-treatment assessment questionnaires (described below), after which patients will receive their randomly assigned 60-minute intervention session (RISE or information/referral, which is referred to as the "Make the Connection" intervention in the informed consent form). In some cases (particularly during the COVID-19 pandemic, given the requirement to not hold face to face meetings), informed consent will be conducted remotely rather than face to face appointment. In those situations, study staff will speak with potential study participants during the phone screening prior to their informed consent/enrollment appointment to ensure that it is safe for participants to receive study materials in the mail, after which two copies of the informed consent (one for the study team, one for the participant to keep) will be mailed to the participant along with an addressed stamped envelope. During the phone screening, study staff will also confirm that it is safe for participants to receive emails, which will be used for telehealth appointments and the distribution of study materials. A videoconference session using VA-approved platforms (e.g., VVC) will be scheduled with the participant, during which the study team member reviews the ICF with the participant. If the participant agrees to sign the ICF, they will hold up the signed ICF page to the computer camera so the study team member can take a screen shot of the signed ICF. The screen shot will be saved directly to our secure project folder (in a file separate from any other data collection) as documentation of the signed ICF. The participant will be asked to mail the signed ICF back to the study team using the provided pre-stamped addressed envelope. If the original signed ICF is received, it will be saved along with the printed screen shot picture of the signed ICF.

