**Female VHA Patient Assessments.** Data collection takes place throughout the study and is modeled after a prototypical Hybrid 1 trial . We will administer a full battery of psychosocial assessment at pre-treatment, post-treatment assessment (i.e., 10-weeks post enrollment), and 1 month follow-up (i.e., 14 weeks post-enrollment) described below under “Measures.” Participants in the RISE condition will also complete four brief measures of empowerment, self-efficacy, patient activation and valued action at the beginning of each RISE session. At the posttreatment and follow-up assessment, patients will complete a brief audio-recorded semi-structured interview about their experiences with their respective intervention. The post-treatment and follow-up assessments will either be conducted by phone or in person, depending on the participant’s preference (thus allowing for them to determine what is most safe and preferable for them). Women will be compensated with

\$25 for completing the pre-treatment assessment. Upon completion of the post-treatment assessment, women will receive \$50 in cash or by check for their time and participation. Upon completion of the follow-up assessment, women will receive a \$75 in cash or by check for their time and participation. A timeline of all measures is available below in Table 4.

Table 4. Timeline of Assessments	Pre	10-week	14-week
Demographics (age, race, sexual orientation, # deployments)	X		
Demographics (relationship status, housing status)	X	X	X
Personal Progress Scale	X	X	X
Patient Activation Measure- Short Form (PAM-13)	X	X	X
Valued Living Questionnaire (VLQ)	X	X	X
Center for Epidemiological Studies- Depression Scale (CES-D)	X	X	X
Health Service Use	X	X	X
The Conflict Tactics Scale-Revised (CTS-2)	X	X	X
PTSD Checklist for DSM-5 (PCL-5)	X	X	X
Patient Health Questionnaire- 15 (PHQ-15)	X	X	X
12-item Short Form Survey (SF-12)	X	X	X
Safety Behaviors Checklist (SBC)	X	X	X
Connor-Davidson Resilience Scale (CD-RISC 25)	X	X	X
Client Satisfaction Questionnaire 8 (CSQ-8)	X	X	X
Depression Anxiety Stress Scale- (DASS)	X	X	X
Coping Strategy Inventory-Short Form (CSI-SF)	X	X	X
Acceptability		X	X
IPV-Related Head Injury	X		

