#### *Data Analyses for Aim 3*

*Qualitative.* The rapid qualitative analyses are time and resource intensive. As such, [name] has budgeted for a full-time project manager and research assistant to ensure timely transcription and analyses of interview data. The coding team will hold weekly meetings focus on analysis and thematic summaries in order to stay on track with the timeline of this study. If additional resources are needed for transcribing focus groups and interview data, and/or for coding, [name] may be able to request additional resources through the Women's Health Sciences Division of the National Center for PTSD and the Center for Healthcare Organization and Implementation Research (e.g., additional PM or RA time for participation in qualitative analysis team). Any such changes would undergo IRB approval prior to initiation of protocol modifications or additions to the team.

*Quantitative.* RISE is designed to be variable-length, with a special focus on empowering women to choose which modules, and relatedly, how many sessions (with an upper limit of 6) are right for her situation and needs. Thus, it is possible that some women may only desire or be able to attend one session, and therefore may only have quantitative data two assessment periods (i.e., pretreatment and posttreatment). We view this pre-post data as acceptable, as this is a pilot test and we will still be able to examine general levels of improvement on outcomes. In addition to examining changes in quantitative variables over time at the group-level, we will be able to graphically examine individual women's trajectories, which will further enable us to meet our Aim 2 goals. That being said, we do expect that the majority of participants will opt for multiple sessions based on the feedback we've received in Phase 1 focus groups with women VA patients. Part of the purpose of this open trial will be to begin to understand how many sessions (and which types of modules) women choose to inform the implementation protocol for the RCT in Phase 3.

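### The 15% loss rate does not turn 68 enrolled into 60 retained: applied to 68 it leaves about 58, and 60 allows at most 8 of 68 (11.76%) lost

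*Combined protocol and SAP*

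**What the plan says.** The sample size reasoning is one sentence in section (c), Method and Data Analysis, under Aim 3: "Assuming 15% loss to follow-up based on current study estimates, we will aim to enroll 68 women to ensure sample size of n=60". The sentence goes on to say whom the 60 comprise: "for participants with post-treatment and/or follow-up assessments (i.e., at least 2 data points").

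The 68 is also a ceiling. The same paragraph says "up to 68 female patients will be recruited and randomly assigned", the Phase 3 aim says "with up to 68 female patients at VA Boston", and the timeline says "Conduct RCT of RISE with WVs (n = up to 68").

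Two other places fix what counts as a data point. The enrolment procedure, in the text following Recruitment Letter Considerations, puts baseline before treatment: "Patients will complete the pre-treatment assessment questionnaires (described below), after which patients will receive their randomly assigned 60-minute intervention session". The paragraph on patient assessments places the later visits: "post-treatment assessment (i.e., 10-weeks post enrollment), and 1 month follow-up (i.e., 14 weeks post-enrollment").

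The figure of 60 is carried into the restated Phase 3 aim and the eligibility paragraph as a range of 60 to 68. The Quantitative Data Analyses section uses it to count 60 x 3 = 180 observations (68 x 3 = 204 at the upper end).

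**The concern.** The sentence presents 60 as the result of enrolling 68 and losing 15%, and says that 68 will *ensure* it. A reader who does the multiplication gets 58. Because 68 is a cap, the text leaves no room to enrol more women to close the gap.

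The trial's validity is not in question. What is at stake is the benchmark for retention. If 58 of 68 women return, loss is 10/68 = 14.7%, within the assumed 15%, yet the promised 60 has been missed. This is also the only place that explains how 68 relates to 60, and the 60 is then reused in the aims, the eligibility text and the observation count.

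**Working it through.** **Inputs.** Loss 15%, enrolment 68 and retained target 60, all from the one Aim 3 sentence. Visits: baseline, week 10 and week 14, from the patient assessments paragraph. No other loss rate, and no other derivation of 68, appears in the document.

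**Step 1: try to reproduce the stated figure.**

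- Forwards, enrolled x (1 - loss): 68 x 0.85 = 57.8, about 58. The stated figure is 60.
- Backwards, target / (1 - loss): 60 / 0.85 = 70.6, so 71 women. The stated figure is 68.
- A common but invalid inflation, target x (1 + loss): 60 x 1.15 = 69. This does not give 68 either.

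The stated pair is not reproduced. The source of 68 is unknown.

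**Step 2: find the loss that 68 and 60 imply.** (68 - 60)/68 = 8/68 = 11.76%. At 12% loss, 68 x 0.88 = 59.84, just under 60.

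**Step 3: check what the 60 counts.** Every woman completes the baseline battery before her session, so two data points means baseline plus at least one later visit. A woman falls outside the 60 only if she misses both week 10 and week 14. On the direct reading, the 15% is the proportion who do so, and Step 1 applies.

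**Step 4: try the single-visit reading.** Suppose the 15% is loss at week 14 only. Then 68 x 0.15 = 10.2 women miss that visit. If a share f of them also missed week 10, the number with two or more data points is 68 - 10.2f, taking the women seen at week 14 as qualifying in any case.

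| f (share also missing week 10) | Women with two or more data points |
|---|---|
| 1 | 57.8 |
| 0.784 | 60.0 |
| 0.5 | 62.9 |
| 0 | 68 |

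Reaching 60 needs f no greater than 8/10.2 = 0.784, so at least 2.2/10.2 = 22% of those missing week 14 must have week-10 data. The plan gives no value of f.

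**Step 5: size the gap.** On the direct reading, (60 - 57.8)/60 = 3.7% fewer women. If standard errors scale with 1/sqrt(n), sqrt(60/57.8) = 1.019, about 1.9% larger.

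**Step 6: test the word *ensure*.** As an illustration, if each woman is retained independently with probability 0.85, the binomial chance of keeping at least 60 of 68 is 0.29.

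**The case against.** The strongest reply is that the 15% has been misread. The plan uses the term follow-up for the visit after post-treatment, and the sentence itself names the two visits separately and counts women who have either. If the 15% means loss at week 14, about 10 women are lost there, and two or three of them with week-10 data are enough to reach 60. The rate is attributed to current study estimates that are not reproduced, so how loss was defined in them cannot be checked. On this view the fault is an undefined rate and not an arithmetic error.

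This reading is plausible, and under it there may be no shortfall. It does not rescue the sentence, because 60 then depends on a second quantity that the plan never states. The nearest support is in section 4.d, under Data Analyses for Aim 3, which foresees that some women "may only have quantitative data two assessment periods (i.e., pretreatment and posttreatment"). It gives no proportion, and the surrounding text refers to the open trial.

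Two smaller objections stand in part. First, the multilevel model is meant to cope with attrition and is not restricted to women with two data points, so the 1.9% is only a rough guide. Second, if 58 becomes the expected number, the 60 used elsewhere needs to remain compatible with it. The count of 180 is built from 60 women at three visits. A separate calculation, 15% loss at each later visit, gives 68 + 57.8 + 57.8 = 183.6 observations. That is a different route to a similar total; it gives no reason to change 180, but it does not derive it.

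**Conclusion.** The concern holds as a minor point. Applied directly to 68, the plan's loss rate yields about 58 women with two or more data points, not the 60 it is said to ensure. The shortfall is about 2 women (3.7%), with standard errors about 1.9% larger under the 1/sqrt(n) assumption, so the effect on power is negligible.

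The size of the gap rests on reading the 15% as the proportion with neither later visit. If it is instead the loss at week 14, there is no shortfall provided at least 22% of the women lost then were seen at week 10. Neither reading gives 60 from the stated figures alone, so the sentence needs correcting either way. The finding does not by itself show that the power statement is wrong.

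**What to change.** Keep 68 as the enrolment target and edit the one sentence in section (c), Aim 3, according to what the 15% means:

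- **If it is the proportion with neither later visit:** drop the claim that 68 ensures 60. Say that about 58 women are expected to have two or more data points at 15% loss, and that 60 requires no more than 8 of 68 (11.76%) to lack both the week-10 and week-14 assessments.
- **If it is loss at the 14-week visit only:** say so, and state the assumed loss of women with neither later visit. That figure must be no more than 8 of 68 for 60 to follow.

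The 60 to 68 range in the Phase 3 aim and eligibility text, and the 180 and 204 observations in the quantitative analysis section, need no change beyond staying consistent with the restated figure.

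The cost is one sentence. Enrolment, design and analysis are untouched; either the stated expected sample falls by about 2 women or the 15% gains a definition.

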### Quantitative Data Analyses (Aim 3)

We will conduct multilevel longitudinal data analyses to examine change in psychosocial outcomes. Time will be coded as 0, 1, and 2 respectively for pretreatment, posttreatment, and 1-month follow-up; therefore, the Level-1 intercept will represent initial status and the Level-2 time coefficient will represent change over time. We will also evaluate a model using linear and quadratic polynomial contrasts and orthogonal contrasts to evaluate non-linear (i.e., non-constant) change. We will add a dummy-coded intervention variable (RISE vs. information/referral condition) as a predictor of the Level-1 change parameters (initial status and change over time) to evaluate the treatment x time interaction (i.e., does group membership moderate change in the outcomes?). This analytic strategy will produce effective and efficient tests of change in outcomes, even in the presence of attrition, and provides us with flexibility to assess and adjust for control variables, if needed (e.g., age, IPV frequency). We will calculate effect size estimates and 95% confidence intervals, which produce an estimate of  $d$  from multilevel analyses that is comparable to  $d$ 's produced using traditional methods (e.g., repeated measures ANOVA). To examine the range of effect sizes that might be reasonable to expect in a future trial, we will calculate effect sizes and 95% confidence intervals for all of our primary and secondary outcomes.

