The study will incorporate a 2 x 3 (Condition: RISE vs. information/referral x Time: pretreatment, post, and 1-month follow-up) mixed-factorial multi-measurement design producing  $N=60 \times 3$  time points = 180 measurement observations (or up to  $N=68 \times 3$  timepoints = 204). The intervention in this study is a difference over and above standard care (not in isolation), so it is expected that the effect will be modest ( $d=.5$ ,  $f^2=.15$ ,  $PV=.1$ ). Traditional approaches to repeated measures can thus be used to assess power. However, the design affords two alternate methods. The interaction term from the multilevel model will have 118 degrees of freedom, given the study design, which is more than sufficient to render a power = .95 for the primary outcomes. A simulation was also conducted leveraging the inputs from the prior studies, assuming a modest effect size, to determine power. In all simulated conditions, power is estimated  $>.80$  for primary outcomes. Consistent with the American Statistical Association recommendations, we will examine effect sizes and 95% confidence intervals, along with p-values in our tests.

We will assess the feasibility and acceptability of RISE and the comparison condition by looking for consistent patterns in rates of intervention attendance (i.e., number of RISE sessions attended) and reasons for RISE termination. We will examine the acceptability of both interventions using data from the CSQ-8 and qualitative data from patient interviews. Provider quantitative measures of feasibility and acceptability will be primarily

descriptive in nature, including mean summary scores and proportion of participants rating the intervention as feasible and acceptable. Lower scores will indicate a need to examine a given dimension more closely. We will integrate qualitative analyses within the quantitative analyses for the purposes of expansion, development, and convergence.

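### The power figures (180 observations, 118 df, .95) assume that all 60 retained women attend all three visits, but the sample-size text counts a woman as retained with two

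*Combined protocol and SAP*

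**What the plan says.** Two places in the combined protocol and SAP use the same n=60.

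- **(c) Method and Data Analysis, Aim 3, randomized trial paragraph.** "Assuming 15% loss to follow-up based on current study estimates, we will aim to enroll 68 women", in order to "ensure sample size of n=60 for participants with post-treatment and/or follow-up assessments (i.e., at least 2 data points"). A woman qualifies with the pre-treatment visit plus either follow-up.
- **Quantitative Data Analyses (Aim 3), power paragraph.** N=60 is multiplied by three: "time points = 180 measurement observations (or up to" 204 for N=68). The df follow: "The interaction term from the multilevel model will have 118 degrees of freedom, given the study design". The paragraph then rests a power of .95 for the primary outcomes on those df. It adds a simulation: "In all simulated conditions, power is estimated" above .80. It does not say whether missed visits were simulated.

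The analysis text gives the time scale: "Time will be coded as 0, 1, and 2 respectively for pretreatment, posttreatment, and 1-month follow-up". Arm is entered as a predictor of initial status and of change over time, and polynomial and orthogonal contrasts are also planned for non-linear change. That text says the multilevel analysis copes with attrition, but it does not carry attrition into the observations, the df or the power.

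**The concern.** A retention target exists to secure the data behind the stated power. Here the target can be met in full with fewer data than the power figure assumes, because the target accepts two visits and the power figure needs three. The trial could report that it reached 60 while holding fewer than 180 observations and fewer than 118 df. A reader would have no way to see the difference.

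The two follow-ups are also interchangeable in the retention rule but not in every planned test. For a linear trend coded 0, 1, 2, the last visit carries most of the information on change. For a curvature contrast, the middle visit is indispensable. A single count of women with either follow-up hides which test has lost information.

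**Working it through.** **Inputs.** From the documents: 60 retained women, 68 enrolled, three visits, 118 df, power .95, and effect size given as d=.5, f²=.15 and PV=.1. Assumed: two-sided 5% test (not stated, but consistent with "we will examine effect sizes and 95% confidence intervals, along with p-values in our tests") and equal arms (the ratio is not stated). Not in the documents: the number k of the 60 women with only two visits, so a range is shown.

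**Step 1: reproduce the df.** Observations minus women minus two within-person terms (time, treatment x time): 180 − 60 − 2 = 118. The alternative (60 − 1)(3 − 1) also gives 118. Both need all 60 women to have all three visits.

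**Step 2: reproduce the power.** Noncentral F(1, v) with λ = v·PV/(1 − PV). With PV=.1 and v=118, λ = 118/9 = 13.11 and power is .949, which matches the stated .95.

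**Step 3: apply the retention rule.** Observations = 180 − k and df = 118 − k. At the limit k=60: 60 x 2 = 120 observations and 120 − 60 − 2 = 58 df.

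**Step 4: power by two methods.**

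- *df-only:* the step 2 formula with the reduced v. It does not distinguish which visit is missed.
- *Linear model:* random intercept, 30 women per arm, within-woman correlation r of .3 to .7 (assumed). Noncentrality is set to 13.21, which gives .95 at 118 df, and is scaled by the relative information on arm x time.

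The linear model shows why the visit matters. From pre and week 10, a woman's slope is (y1 − y0)/1, with variance 2σ²(1 − r). From pre and week 14, it is (y2 − y0)/2, with variance σ²(1 − r)/2. The first has four times the variance of the second.

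| k of 60 | Observations | df | Power, df-only | Linear model, week 14 missed | Linear model, week 10 missed |
|---|---|---|---|---|---|
| 0 | 180 | 118 | .949 | .950 | .950 |
| 9 (15%) | 171 | 109 | .932 | .926-.929 | .950 |
| 15 (25%) | 165 | 103 | .918 | .904-.910 | .950 |
| 30 (50%) | 150 | 88 | .871 | .818-.833 | .949 |
| 60 (100%) | 120 | 58 | .704 | .431 | .947 |

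**Step 5: sensitivity to the model.** The plan does not say whether slopes are random. With a slope variance of half the residual variance (assumed), the bottom-row figure for missing week 14 is .62 instead of .43.

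**Step 6: the women not retained.** The other 8 (68 − 60) add at most 8 baseline-only observations. In the random-intercept model they raise the information on arm x time by about 2-4%.

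**The case against.** The strongest reply is that the effect is small at any likely level of loss, and that reply largely stands. Participants must be willing to attend all assessments, follow-ups can be done by phone, and the last visit carries the largest payment. If the plan's 15% is read as the loss at each follow-up among all 68, the count is 68 + 2 x 57.8 = 183.6 observations and 183.6 − 68 − 2 = 113.6 df, where the df-only method gives about .94. Power falls below .80 only from 46 two-visit women by the df-only method, or when roughly 54-58% of the 60 miss week 14 in the random-intercept model.

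Second, 204 is introduced as an upper figure and the df as what the design yields, so the paragraph can be read as describing complete data. That is a fair reading, but the paragraph never says so, and it attaches the .95 to those figures.

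Third, the .95 depends on the effect input. With f²=.15 and one numerator df, the df-only method gives .987 at 118 df and still .949 at k=30. With d=.5 taken as f²=.0625, it gives .768 and .640. That the three effect sizes disagree is a separate matter. PV=.1 is used here because it reproduces the stated figure. Whichever is used, power falls as visits are missed.

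That multilevel models tolerate attrition is true of validity. It does not restore the missing information.

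A reader might infer that the retention target should become 60 women with the 14-week visit. The documents do not support that. No text makes week 14 primary, the planned non-linear contrasts need week 10, and 68 x .85 = 57.8 would miss such a target on the plan's own loss assumption.

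**Conclusion.** The inconsistency holds. The same 60 women are defined by at least two visits in one place and credited with three in another. On the effect input that reproduces it, the .95 tied to 118 df is an upper bound: the retention rule allows 120 to 180 observations and 58 to 118 df.

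The size is modest at plausible loss: about .90-.93 if 15-25% of the 60 lack week 14, and about .82-.87 at 50%. If week 10 is the missed visit, the linear term loses almost nothing. These figures rest on an assumed two-sided 5% test, equal arms, an assumed missing share and the models described above.

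Two stronger readings are not supported. One is that power collapses to .43: that needs every retained woman to miss week 14 under a random-intercept linear model, and the same extreme gives .62 with the random slope tried here or .70 by df alone. The other is that the simulated power above .80 is wrong: its missing-visit inputs are not given, so it can be neither confirmed nor faulted.

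**What to change.** In the power paragraph of Quantitative Data Analyses (Aim 3):

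- State an expected completion rate for week 10 and for week 14, consistent with the retention rule in (c) Method and Data Analysis, and recompute observations, df and power at those rates.
- Keep 180, 118 df and .95, and also 204, only if labelled as complete-data ceilings. Give the range that the retention rule allows: 120 to 180 observations and 58 to 118 df from the 60 women.
- Say whether the simulation included missed visits, and at what rates.

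When reporting, give retention separately for weeks 10 and 14. Leave the retention target and the enrolment of 68 as they are.

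The cost is a few sentences and one rerun of the existing power calculation or simulation. The only downside is a slightly less favourable stated power. No women, visits or staff are added.
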